## 22.5.3. Efficacy Variables

The annualized bleed rate (ABR) is the primary endpoint for testing the primary objective of the study, as well as for testing one of the secondary objectives of the study. ABRs will reflect the incidence of bleeds treated with FVIII replacement therapy. To avoid potential bias related to prior treatment, the first month of each protocol-defined prophylaxis treatment will serve as a washout period; ABR analyses will be performed with and without data from this washout period.

- For the primary objective of demonstrating that moroctocog alfa (AF-CC) prophylaxis reduces the ABR relative to on-demand therapy, the null hypothesis is that prophylactic treatment does not reduce the ABR relative to on-demand treatment. The alternative hypothesis is that prophylactic therapy does reduce the ABR.
- To test the hypothesis, an analysis of variance (ANOVA) will be conducted to compare the mean ABR between subjects in on-demand (segment 1) and prophylaxis (segment 2) treatment regimens. Only subjects who practice on-demand therapy with moroctocog alfa (AF-CC) during segment 1, before starting the protocol-defined moroctocog alfa (AF-CC) prophylaxis in segment 2, will be included in this analysis. The ANOVA will include factors for treatment regimen (study segment 1 or 2). The model will also include a blocking factor for subjects to ensure that the comparison of ABRs from each treatment regimen is performed on a within subject basis. The p-value for treatment regimen calculated in ABR of the ITT population will be used to test the null hypothesis; a p-value less than 0.05 will be considered significant.
- For the secondary objective of assessing the effect of a high- versus low-frequency dosing schedule on the efficacy of moroctocog alfa (AF-CC) prophylaxis, the null hypothesis is that there is a difference in mean ABR between the two prophylaxis regimens. The alternative hypothesis is that the two prophylaxis regimens are similar enough to be considered clinically equivalent. To test this hypothesis, the two protocol-defined prophylaxis regimens (a high- and a low-frequency dosing regimen) will be assessed in a crossover design. Only subjects who practice protocol-defined prophylaxis regimens in segment 1 and 2, respectively: the low- followed by the high-frequency dosing regimen (AB), or the high- followed by the low-frequency dosing regimen (BA) will be included in this analysis.

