## 22.6. Interim Analysis and Report

An independent E-DMC will periodically review data from the study to ensure subject safety, with review intervals of approximately every 6 months. See Section 17 for more information regarding the E-DMC.

Prior to study completion, selected (safety, efficacy and/or PK) data from this study may be summarized and reported to regulatory authorities to support regulatory submissions or requests. The analyses for these summaries would be based on descriptive statistics.

Per discussions with the FDA, a final report for the OD cohort will be submitted comparing prophylaxis efficacy and safety versus on-demand therapy according to section 3.3 of the statistical analysis plan. Additionally, after approximately 38 evaluable RP subjects, who practiced prophylaxis for both segment 1 and segment 2, complete the study, a final report for the RP cohort will be submitted.

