For the RP cohort, the comparison of high- versus low-frequency prophylaxis dosing schedules, a subset analysis of data from the completed ReFacto PUP study (Wyeth protocol 3082A1-301-WW) revealed an ABR of 5.7 ±5.2 (N=26) in patients receiving a high-frequency prophylaxis regimen (3 infusions per week) compared to an ABR of 7.1 ±4.1 (N=13) in patients receiving a lower-frequency prophylaxis regimen (2 infusions per week). However, the treatment assignment was not randomized and prophylaxis regimens were not controlled in that study. To avoid selection bias and inter-patient variability affecting outcome, two protocol-defined prophylaxis regimens (a high- and a low-frequency dosing regimen) will be assessed in a crossover design. Assuming an intraclass correlation of 30% and a standard deviation of 6 bleeds per year based on this previous ReFacto PUP study, a within-subject standard deviation of 5 bleeds per year was used for sample size calculations for the comparison between the two protocol-defined prophylaxis regimens (A and B). Given this, 36 RP subjects are needed to provide 80% power to demonstrate equivalence of the two regimens (see Section 22.5.3 for description of statistical analysis).

Allowing for an attrition rate of 25%, approximately 48 RP subjects need to be enrolled to support this objective.

Based on a sample size re-estimation using data from this ongoing study, a difference of means of 1.3 bleeds per year between the two protocol-defined prophylaxis regimens (A and B) with a corresponding standard deviation of the difference of 6.5 was obtained requiring 38 subjects to provide 80% power to demonstrate equivalence of the two regimens. Allowing for an attrition rate of 30%, approximately 56 RP subjects need to be enrolled. The two prophylaxis regimens will be considered equivalent if the limits of the 2-sided 90% confidence interval for the difference in observed mean ABRs fall wholly within the interval defined by fewer than 4 bleeds per year.

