1. The first interim CSR presented safety, efficacy and baseline data for subjects at Site PP separately from data for subjects at other sites, due to serious breaches of GCP compliance by the investigator and study staff at Site PP pertaining to data integrity. As implemented in the second Interim CSR, in the Final CSR, safety, efficacy and baseline summary data will be presented excluding Site PP with the exception of protocol deviations, recovery/pharmacokinetic data, and inhibitor incidence, which include all sites.

- 2. As determined for the second Interim CSR for the study's primary endpoint analysis in the OD cohort only, a linear mixed-effects model with unstructured variance-covariance matrix provides a more robust model for the comparison of annualized bleeding rate (ABR) given the nature of the study data, while still controlling for the same factors as specified in the SAP ANOVA model. This model allows for the inclusion of all intent-to-treat (ITT) subjects with ABR data and also takes into account the correlation between the 2 within-subject measurements of ABR at each segment. Because all enrolled subjects had severe (<1%) hemophilia at baseline (ie, just one level of the factor was present and therefore not informative), hemophilia severity is not included as a factor in the model as planned. In the Final CSR, the estimates of the ABR for each regimen (segment) and for the difference as well as the corresponding two-sided 95% confidence intervals (CIs) will be reported using the linear mixed-effects model described above rather than as described in SAP Section 3.3.1.2.

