- 3. As implemented in the second Interim CSR as per FDA Written Response dated 28 January 2016 (CRMTS #10042, BL 125264/1540), supportive analyses will also be performed for the ITT population for the Final CSR. A paired t-test will be used to test the within-subject change in ABR for the subjects who will be evaluated with both OD and routine prophylaxis (RP) dosing during the study. In addition, a one-sided 95% CI for the ratio of the arithmetic means for ABR during RP over the ABR during OD treatment will be calculated. Ogawa's parametric confidence interval for the ratio of two paired means¹ assumes the ABR is bivariate normally distributed for RP and OD treatments and will be calculated using R statistical software (version 3.2.3). If the one-sided 95% upper confidence bound is ≤0.5, then this will confirm that the ABR during RP treatment was at least 50% lower than that observed during OD treatment.
- 4. In accordance with FDA correspondence dated 27 January 2017 (IND 10040/246) stating that a non-inferiority clinical margin M2 of 3 bleeds or fewer per year may be adequate, equivalence between the 2 RP regimens will be declared if the limits of the 90% two-sided confidence interval fall wholly within the interval of (-3, 3) bleeds per year, rather than protocol/SAP specified (-4, 4) (SAP Sections 1.4.2 and 3.3.2.2).
- 5. Per FDA correspondence dated 27 January 2017 (IND 10040/246), incidence rate of inhibitor development will be additionally described by number of prior exposure days at study entry. For this assessment, based on the risk of the inhibitor development according to the number of exposure days, minimally treated patients (MTPs) will include those who had accrued 20 to <50 exposure days to any FVIII replacement product prior to enrollment into Protocol B1831001. Note: Previously treated patients (PTPs) are patients who have received FVIII replacement therapy. Prior to Protocol Amendment 4, PTPs were defined for the purposes of the study as those who had accrued at least 50 exposure days (EDs) to any FVIII replacement product prior to study enrollment. To improve enrollment, in Protocol Amendment 4 (dated 15 September 2009) this number was decreased to at least 20 prior EDs for inclusion in the study. SAP Section 3.4.2.1 refers to Inhibitor Development.

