1.4.2. Sample Size Estimation Comparing High versus Low Prophylactic Dosing

A secondary objective is to evaluate the effect of a high versus low dosing frequency schedule on prophylactic efficacy. Data from the previously mentioned moroctocog alfa study 301 revealed an ABR of 5.7 ± 5.2 (N=26) in subjects receiving a high-frequency prophylaxis regimen (3 infusions per week) compared to an ABR of 7.1 ± 4.1 (N=13) in patients receiving a lower-frequency prophylaxis regimen (2 infusions per week). Assuming an intraclass correlation of 30% and a standard deviation of 6 bleeds per year based on the above study results, a within-subject standard deviation of 5 bleeds per year was used for sample size calculations for the comparison between the high- and low-frequency prophylaxis regimens. Given this, 36 RP subjects are needed to provide 80% power to demonstrate equivalence of the two regimens. The two regimens will be considered equivalent if the limits of the 90% two-sided confidence interval for the difference in observed mean ABRs falls wholly within the interval of -4 to 4 bleeds per year. Allowing for an attrition rate of 25%, approximately 48 RP subjects should be enrolled to support this objective.

Based on a sample size re-estimation using data from this ongoing study, a difference of means of 1.3 bleeds per year between the two protocol-defined prophylaxis regimens (A and B) with a corresponding standard deviation of the difference of 6.5 was obtained requiring 38 subjects to provide 80% power to demonstrate equivalence of the two regimens. Allowing for an attrition rate of 30%, approximately 56 RP subjects need to be enrolled. The two prophylaxis regimens will be considered equivalent if the limits of the 2-sided 90% confidence interval for the difference in observed mean ABRs fall wholly within the interval defined by fewer than 4 bleeds per year. See the Summary of Changes to Planned Analyses for the Final CSR (Item 4) for further discussion.

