3.3.2.2. Analysis Method

The null hypothesis is that there is a difference in ABR between the two prophylaxis regimens. The alternative hypothesis is that the two prophylaxis regimens are similar enough to be considered clinically equivalent.

The 90% 2-sided confidence interval (CI) for the mean difference in ABRs for the 2 prophylaxis regimens for ITT subjects will be constructed using the t distribution with n-1 degrees of freedom (n equals the number of subjects) to assess the equivalence of these 2 regimens. Equivalence will be demonstrated and the null hypothesis rejected if the limits of the 90% CI fall wholly within the interval of (-4, 4) bleeds per year. See Summary of Changes to Planned Analyses for the Final CSR (Item 4) for further discussion.

Additionally, an ANOVA model appropriate for the crossover design will be employed to test for the presence of treatment sequence, period and carryover effects. The ANOVA model will be fitted with terms for treatment sequence (AB or BA), treatment frequency (A or B), period (study segment 1 or 2), carryover and subject nested in treatment sequence. If one or more of the terms for treatment sequence, period or carryover are statistically significant then exploratory analyses may be prepared to help understand the nature of the effect. See Summary of Changes to Planned Analyses for the Final CSR (Item 6) for further discussion.

ABR will also be presented as descriptive statistics (n, mean, SD, median, interquartile range, minimum, and maximum). ABRs will be summarized by bleed type (ie, spontaneous or traumatic), by bleed location (eg, joint, soft tissue/muscle), and by treatment frequency (ie, prophylaxis A, prophylaxis B).

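### The RP equivalence margin was tightened to ±3 bleeds per year, but the only stated power is for ±4; on the plan's own inputs it falls from about 81% to about 47% at 38 subjects

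*SAP*

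**What the plan says.** SAP 1.4.2 and Protocol 22.7 report a sample size re-estimation from the ongoing study. The difference in mean ABR between regimens was 1.3 bleeds per year, and a "standard deviation of the difference of 6.5 was obtained requiring 38 subjects to provide 80% power to demonstrate equivalence of the two regimens". Protocol 22.7 continues: "Allowing for an attrition rate of 30%, approximately 56 RP subjects need to be enrolled". In the same paragraph the SAP gives the criterion for that calculation: the 90% confidence limits must "fall wholly within the interval defined by fewer than 4 bleeds per year". The Protocol Synopsis repeats these figures.

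SAP 3.3.2.2 sets out the analysis. The 90% interval for the mean difference "for ITT subjects will be constructed using the t distribution with n-1 degrees of freedom (n equals the number of subjects".

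The SAP's Summary of Changes to Planned Analyses for the Final CSR, Item 4, then replaces the margin, citing FDA correspondence of 27 January 2017. Equivalence now requires the limits of the "90% two-sided confidence interval fall wholly within the interval of (-3, 3) bleeds per year, rather than protocol/SAP specified (-4, 4". Item 4 names SAP 1.4.2 and 3.3.2.2 as the affected sections, and both refer the reader to it. It gives no power and no sample size for the new margin.

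The timing of the final RP report is unchanged: it follows "after approximately 38 evaluable RP subjects, who practiced prophylaxis for both segment 1 and segment 2, complete the study" (Protocol 22.6; the same in SAP 1.3.4).

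**The concern.** The Summary of Changes is not a history of superseded text. The SAP Overview presents it as the set of changes that govern the final report and that were decided after Amendment 10, so (-3, 3) is the operative rule. Every planning figure for the RP comparison nevertheless belongs to (-4, 4). A reader who follows the pointer from SAP 1.4.2 to Item 4 finds a new margin and nothing on what it does to power.

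This is the only powered comparison in the RP cohort. If the interval misses ±3, a reader who has seen 80% power may take the miss as evidence that the regimens differ. Under the plan's own assumptions and 38 subjects, a miss was slightly more likely than a success before any data were analysed.

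**Working it through.** **Inputs**
- True difference d = 1.3 and SD of the within-subject difference s = 6.5 bleeds per year (SAP 1.4.2, Protocol 22.7).
- Two-sided 90% interval from t with n − 1 degrees of freedom, that is, two one-sided tests at 5% each (SAP 3.3.2.2).
- n = 38 evaluable. The attrition allowance gives 56 × 0.70 = 39.2, so about 39. Going the other way, 38/0.70 = 54.3, so 55, against a stated figure of about 56.
- Margin M = 4 (SAP 1.4.2) or M = 3 (Item 4).

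**Method.** Equivalence is declared when |observed mean difference| + t(0.95, n−1) × (observed SD)/√n < M. Power is the probability of that event when the mean difference is normal with mean d and standard error s/√n, integrated over the chi-square distribution (n − 1 df) of the sample variance. This is exact for normally distributed differences.

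**Step 1: reproduce the plan (M = 4).** Power is 79.7% at n = 37 and 80.7% at n = 38, so 38 is the smallest n reaching 80%. This matches the stated figure and confirms both the method and that the 80% belongs to ±4.

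**Step 2: change only the margin (M = 3).**

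| n | Power at ±4 | Power at ±3 |
|---|---|---|
| 38 | 80.7% | 46.6% |
| 39 (56 less 30%) | 81.6% | 47.6% |
| 56 (all planned subjects) | 92.3% | 61.3% |

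The smallest n with 80% power at ±3 is 92. Simulation agrees (46.5% to 46.6% at n = 38, ±3).

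**Step 3: a hand check.** At n = 38 and SD 6.5, the half-width is t(0.95, 37) × 6.5/√38 = 1.687 × 1.054 = 1.78. To meet ±3 the observed difference must therefore lie within 3 − 1.78 = 1.22 of zero, which is less than the re-estimated 1.3. An observed 1.3 would give 1.3 ± 1.78 = (−0.48, 3.08), inside ±4 and outside ±3. At n = 39 the upper limit is 3.05. The first n at which it drops below 3 is 42 (upper limit 2.99).

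**Step 4: sensitivity (my assumptions; M = 3, n = 38).**
- True difference 1.0: 56.7%. True difference 0: 74.9%.
- Difference 1.3 with SD 5.5, 6.0 and 7.0: 58.8%, 52.4% and 41.1%.
- Fewer subjects, difference 1.3, SD 6.5: 44.5% at n = 36 and 42.3% at n = 34.

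**Step 5: type I error.** At a true difference of exactly 3, the chance of meeting ±3 with n = 38 is 5.0%. The new margin is sound in that respect.

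**The case against.** **The documents do not hide the change.** SAP 1.4.2 states the margin of 4 beside the 80% and sends the reader to Item 4, which says openly that 3 replaces 4. Protocol Amendment 10 is dated October 2015, before the 2017 correspondence, so its text could not have anticipated the change. All of this is right, and the 80% is not a miscalculation. It explains why the body was left alone, but not why Item 4, written for this change and citing 1.4.2, omits its effect on power.

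**The analysis n need not be 38.** The analysis uses ITT subjects, and SAP 3.3.2.1 ends the days on treatment at the last visit for anyone who does not complete a segment. A subject who leaves during segment 2 can therefore still supply an ABR for both regimens. The figure of 38 is a reporting trigger, not a cap. This stands: n could plausibly fall between 38 and 56. At the plan's inputs, however, power at ±3 over that range runs only from 47% to 61%. It could also be lower. Protocol 22.5.3 limits the comparison: "Only subjects who practice protocol-defined prophylaxis regimens in segment 1 and 2, respectively" are included. Item 1 of the Summary of Changes adds that "efficacy and baseline summary data will be presented excluding Site" data from one non-compliant centre; its number of RP subjects is not given, so no size can be put on that loss.

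**Kinder assumptions restore the power.** With no true difference, power at ±3 is 86% at n = 47 and 92% at n = 56. That is correct, but it sets aside the sponsor's own re-estimate of 1.3, the value that justified 38 subjects. The 1.3 is itself a point estimate with no interval given, so 47% should be read as a planning figure rather than a precise one. Whether a miss is more likely than a success also turns at n = 42 (50.4%).

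**It is a secondary objective, and the estimate and interval will show the precision achieved.** Both are true. They limit the consequence but do not supply the missing statement.

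**Conclusion.** The concern holds. The rule for the final report is (-3, 3), and the only stated power and size belong to (-4, 4). Under the plan's difference of 1.3 and SD of 6.5, power at 38 subjects is about 47%, not 80%. It stays at or below 61% for any n up to the 56 planned. At n = 38, even a true difference of zero gives only 75%. These figures assume normally distributed within-subject differences and the paired t interval in SAP 3.3.2.2. The problem lies in what the plan says about its own power; the validity of the test and the choice of margin are not in question. It is worth correcting because a miss at ±3 will be read against the stated 80%.

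**What to change.** In SAP 1.4.2, label the statement of 38 evaluable, 80% power and about 56 enrolled as derived for the (-4, 4) margin only. Do the same in Protocol 22.7 and the Synopsis when the protocol is next changed. Add to Item 4:

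> The sample size was not re-derived for (-3, 3). With a true difference of 1.3 and an SD of the difference of 6.5, power to meet (-3, 3) with about 38 evaluable subjects is about 47%.

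If the sponsor wants a range, it can add 57% (difference 1.0), 75% (difference 0) and 61% (difference 1.3, all 56 analysed), each labelled as a sensitivity value with its assumptions.

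The cost is two sentences and a short label. Margin, test, enrolment and data collection do not change. The only downside is a less favourable stated power.

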- 6. For the exploratory analysis in RP cohort subjects, to test for the presence of treatment sequence, period and carryover effects, SAP Section 3.3.2.2 states that the ANOVA model will be fitted with terms for treatment sequence (AB or BA), treatment frequency (A or B), period (study segment 1 or 2), carryover and subject nested in treatment sequence. However, this model is overparameterized. Instead, the more appropriate mixed-effect model ABR=sequence period treatment, with subject as a random effect will be used to evaluate the treatment effect. Contrasts will be constructed to test if the carryover effect for each sequence is the same, and if the same, if that carryover effect is equal to zero.
- 7. Protocol Amendment 10 has text in section 15.2 (also appears in SAP Section 2.2) which states that the pharmacokinetic dose will be prepared from a single lot. However, multiple lots were used over the course of this study.
- 8. Protocol Amendment 10 has text in sections 22 and 22.6 (also appears in SAP Section 3) which indicates that both efficacy and safety will be reported separately for the 2 cohorts (OD and RP). However, only efficacy data is presented separately, and safety data is presented for all subjects combined.

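### SAP Item 6 infers equal carryover from a low-powered non-significant test, then tests a common carryover that an AB/BA design cannot estimate

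*SAP*

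**What the plan says.** SAP 3.3.2.2 plans a crossover ANOVA with terms for sequence, treatment, period, carryover and subject within sequence. It adds: "If one or more of the terms for treatment sequence, period or carryover are statistically significant then exploratory analyses may be prepared". Item 6 of the Summary of Changes recognises that this model has too many parameters. It substitutes a smaller one: "the more appropriate mixed-effect model ABR=sequence period treatment, with subject as a random effect will be used to evaluate the treatment effect". Item 6 then adds the carryover step: "Contrasts will be constructed to test if the carryover effect for each sequence is the same, and if the same, if that carryover effect is" (zero). The whole analysis is introduced as exploratory: "For the exploratory analysis in RP cohort subjects, to test for the presence of treatment sequence, period and carryover effects".

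Neither place gives a significance level for the contrast, a bound below which carryovers count as the same, or a plan to report a carryover estimate with an interval.

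The equivalence decision is separate. It uses a two-sided 90% CI for the within-subject A-B difference in ITT subjects, with t on n-1 degrees of freedom. Under Item 4 the limits must "fall wholly within the interval of (-3, 3) bleeds per year, rather than protocol/SAP specified (-4, 4").

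The plan also has a first-month check. Protocol 22.5.3 treats the first month of each prophylaxis regimen as a washout and calls for ABR analyses with and without it. SAP 3.3.2.1 specifies the version without it only for the per-protocol population.

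**The concern.** With no other criterion stated, the second contrast in Item 6 is reached only when the first fails to reject. Failure to reject is thereby treated as equality, in support of an objective that is itself an equivalence claim. The first contrast compares subjects, not segments within subjects, so it forgoes the precision that the crossover was chosen for. The second asks for a quantity that the model may not contain.

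What is at stake is the carryover statement that accompanies the equivalence result. Unequal carryover biases the A-B difference, and the 90% CI makes no allowance for it. A report that found the contrast non-significant could describe the interval as free of carryover on almost no evidence.

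**Working it through.** **The plan's own figure.** SAP 1.4.2 gives 38 subjects for 80% power with a difference of 1.3, SD of the difference 6.5, a margin of 4 and a 90% CI. A paired two one-sided t procedure gives about 81% power at n = 38 and just under 80% at 37, so 38 reproduces.

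**What the two contrasts estimate.** Let π1 and π2 be the period effects, τA and τB the regimen effects, and λA and λB the effects each regimen carries into segment 2. The expected ABRs are:

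| Sequence | Segment 1 | Segment 2 |
|---|---|---|
| AB | μ + π1 + τA | μ + π2 + τB + λA |
| BA | μ + π1 + τB | μ + π2 + τA + λB |

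- Difference between sequences in two-segment totals: λA - λB = L. Reading it as carryover assumes no true sequence effect, which randomization supports.
- Average within-subject A-B, with equal sequences: (τA - τB) - L/2. So L = 3 shifts A-B by 1.5, and L = 6 shifts it by 3.
- If λA = λB = λ, both segment 2 cells contain π2 + λ. The data identify only π2 + λ - π1. Adding a common-carryover column to the sequence, period and treatment model leaves the rank at 4, because that column is the period column. The contrast with zero is therefore not estimable.

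**Inputs for the power of the first contrast.**
- n = 38 evaluable, allocated 1:1, so 19 per sequence (SAP 1.3.3 and 1.3.4).
- SAP 1.4.2: "Assuming an intraclass correlation of 30% and a standard deviation of 6 bleeds per year", and SD of the difference 6.5 from the re-estimation.
- These do not agree exactly, so three combinations are used. SD of the difference = σ√(2(1-ρ)). Setting it to 6.5 with ρ = 0.3 gives σ = √(42.25/1.4) = 5.49. Setting it to 6.5 with σ = 6 gives ρ = 1 - 42.25/72 = 0.41.
- Level: not stated. Two-sided 0.05 is assumed, with 0.10 as the alternative.

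**Formulas.** SD of the total = σ√(2(1+ρ)). SE of L = SD of the total × √(2/19). Power is from the noncentral t with 36 df. The 90% half-width for the implied shift is 1.688 × SE / 2.

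For σ = 6 and ρ = 0.3: SD of the total = 6 × √2.6 = 9.67; SE = 9.67 × 0.324 = 3.14; half-width = 1.688 × 3.14 / 2 = 2.65.

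| σ, ρ | SE of L | Missed, L = 3 (0.05 / 0.10) | Missed, L = 6 (0.05 / 0.10) | 90% half-width of shift |
|---|---|---|---|---|
| 5.49, 0.30 | 2.87 | 83% / 73% | 47% / 34% | 2.4 |
| 6, 0.30 | 3.14 | 85% / 75% | 54% / 41% | 2.65 |
| 6, 0.41 | 3.27 | 86% / 77% | 57% / 44% | 2.8 |

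As a check, 40,000 simulated trials with σ = 6, ρ = 0.3 and L = 6 missed 54.0%, with a mean A-B shift of 3.00 in size. If all 56 enrolled boys supplied both segments, the miss rate at L = 6 and level 0.05 would still be 30-41%.

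**The case against.** The strongest reply is that nothing turns on this step. It is labelled exploratory, and the equivalence CI is computed and judged whatever the contrast shows. That stands. No passage says a non-significant result will be cited as proof of no carryover, and the SAP 3.3.2.2 sentence permits follow-up without forbidding it otherwise.

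Nor is the contrast the plan's only protection, as a reader might infer. The first-month-excluded analysis does not depend on any significance test. The switch visit requires at least 72 hours without FVIII (Protocol 15.1.8), the regimens use the same drug at about the same weekly dose, and each segment lasts 12 months. Residual drug at the switch is therefore addressed. What remains is that the first-month analysis is specified in the SAP only for the per-protocol population and can remove only effects confined to that month.

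The L = 6 case is also extreme: it is about the whole mean ABR of 5.7 to 7.1 in the planning study (SAP 1.4.2). This too stands, so the L = 3 figures are the more practical ones, and there the contrast is weaker still.

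Finally, a reader might infer that the step inflates false equivalence claims, since a true difference of 3 masked to 1.5 by L = 3 would pass the interval about 40% of the time instead of 5%. That inflation comes from bias in the interval itself and would occur with or without this contrast. Unequal carryover can equally push A-B away from zero. The figure is no measure of this defect.

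**Conclusion.** The point holds for the exploratory carryover step as written. Non-significance of the first contrast cannot support equal carryover: about 83-86% of differences of 3 bleeds per year and 47-57% of differences of 6 would be missed at 0.05, and about 73-77% and 34-44% at 0.10. The second contrast is not estimable and would be a test of period under another name.

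These rates assume 19 boys per sequence, normally distributed ABRs, the plan's variance figures and a significance level that the documents do not give.

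The consequence is limited to what is said about carryover. The documents do not show that carryover is large, and they do not let this test change the equivalence decision. The correction is worth making because the stated analysis is invalid, not because the equivalence rule is compromised.

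**What to change.** - In Item 6, delete the second half of the carryover sentence, which tests a common carryover against zero.
- Whatever the p-value, report the carryover (sequence) difference with its 90% CI, and half of each as the implied shift in A-B, set beside the (-3, 3) margin. The significance condition in SAP 3.3.2.2 should not govern this.
- State that a non-significant contrast is not evidence of no carryover.
- Extend the first-month-excluded ABR analysis in SAP 3.3.2.1 to the ITT population, consistent with Protocol 22.5.3.
- Leave the equivalence rule unchanged.

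A segment-1-only comparison of A and B is optional. Its 90% half-width would be about 3.0 to 3.3 (for example 5.49 × √(2/19) × 1.688 = 3.0), so it adds little.

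The cost is SAP wording and a few table rows from data already collected. The downside is that the implied-shift interval will be wide, about ±2.4 to 2.8 bleeds per year, or most of the margin. That width shows how little the trial can say about carryover, which a p-value alone would hide.
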